**NEW YORK UNIVERSITY SCHOOL OF MEDICINE**

A prospective, open-label study to evaluate the safety and efficacy of Lap-Band® Adjustable Gastric Band (LAGB®) Operations in the Treatment of Morbidly Obese Adolescents (Ages 14-17)

PROTOCOL DATE:	April 27, 2004	
AMENDMENT No 1:	January 05, 2005	NCT00587301
AMENDMENT No 2:	February 23, 2005	study 11876
AMENDMENT No 3:	April 15, 2005	
AMENDMENT No 4:	May 25, 2006	
AMENDMENT No 5:	July 03, 2008	
AMENDMENT No 6:	June 10, 2010	
AMENDMENT No 7:	January 28, 2011	
AMENDMENT No 8:	December 22, 2011	
AMENDMENT No 9:	May 01, 2012	
AMENDMENT No 10:	July 17, 2013	

PRINCIPAL

INVESTIGATOR: [name] [name].
Director, Program for Surgical Weight Loss
NYU School of Medicine
[name]
[name]

CO-INVESTIGATORS:

[name].
Department of Surgery
NYU School of Medicine

[name].
Department of Surgery
NYU School of Medicine

[name].
Department of Surgery
NYU School of Medicine

[name].
NYU Child Study Center
NYU School of Medicine

Property of New York University School of Medicine

CONFIDENTIAL

This document is a confidential communication of NYU School of Medicine. Acceptance of this document constitutes the agreement by the recipient that no unpublished information contained herein will be published or disclosed without the prior written approval of NYU School of Medicine, except that this document may be disclosed to appropriate institutional review boards/ethical committees so long as they are requested to maintain its confidentiality.

PROTOCOL SUMMARY

Lap-Band® Adjustable Gastric Band (LAGB®) Operations in the Treatment of Morbidly Obese Adolescents (ages 14-17)

- TITLE OF STUDY:** A prospective, open-label study to evaluate the safety and efficacy of Lap-Band® Adjustable Gastric Band (LAGB®) Operations in the Treatment of Morbidly Obese Adolescents (Ages 14-17)
- PRINCIPAL INVESTIGATOR:** [name] [name].
General Laparoscopic Surgery
Director, Program for NYU Langone Weight Management
NYU School of Medicine
[name]
[name]
- PERIOD OF TRIAL:** Jan 2005 –Jan 2019
- STUDY OBJECTIVES:** Is to demonstrate the safety and efficacy of the use of the LAP-BAND® System in the morbidly obese adolescent population in the United States, and therefore provide these individuals with a significantly less morbid and reversible surgical option for weight loss.
- STUDY VARIABLES:** The primary efficacy variable is weight loss evaluated in terms of % excess weight loss (EWL).
- DESIGN:** Prospective, open-label, and single center
- INCLUSION CRITERIA:**
- Be at least 14 and less than 18 years of age at the time of enrollment into the study.
 - Have a BMI of at least 40.
 - Have a history of obesity for at least 5 years, including failed attempts at diet and medical management of obesity.
 - Confirmation by a psychologist or psychiatrist experienced with adolescents that the subject is sufficiently mature emotionally to comply with the study protocol.
 - Express willingness to follow protocol requirements.
 - Assure investigators that subject, if female of childbearing potential, is using an appropriate form of contraception.
- EXCLUSION CRITERIA:**
- Intention or need to have another surgical procedure for weight reduction within 12 months of Lap Band placement.
 - History of congenital or acquired anomalies of the G.I. tract, such as; congenital or acquired intestinal telangiectasia, Crohn's disease or ulcerative colitis; severe cardiopulmonary disease or severe coagulopathy; hepatic insufficiency or cirrhosis.
 - Presence of dysphagia or documented esophageal dysmotility.
 - Patients with autoimmune connective tissue disorders.
 - Patients with acute abdominal infections.
 - Pregnancy or intention of becoming pregnant in the next 12 months.
 - Presence of psychiatric problems or immaturity which would compromise cooperation with the study protocol.
 - History of previous bariatric surgery, intestinal obstruction or adhesive peritonitis.
 - Presence of localized or systemic infection at the time of surgery.

Lap-Band® Adjustable Gastric Band (LAGB®) Operations in the Treatment of Morbidly Obese Adolescents (ages 14-17)

- Chronic use of aspirin and/or non-steroidal anti-inflammatory medications and unwillingness to discontinue the use of these concomitant medications.
- History of gastric or esophageal surgery.
- Use of weigh loss medications simultaneously.

NUMBER OF SUBJECTS: 120

PRODUCT NAME (USAN) LAP-BAND® Adjustable Gastric Band (LAGB®) System

TEST ARTICLE: LAP-BAND® System

DURATION OF THERAPY: 5 years

TABLE OF CONTENTS

1.0 INTRODUCTION

1.1 Background and Rationale

The Lap-Band System is approved by the FDA for use in adults. Studies have demonstrated that childhood obesity increases the likelihood of developing numerous co-morbid conditions, including: hypertension, diabetes mellitus, pulmonary complications, growth acceleration, dyslipidemia, musculoskeletal problems, psychosocial problems, and cancer [1-2]. The severely obese patient faces death without proper treatment of the condition. Furthermore, the economic impact of obesity is substantial. It is estimated that the cost of obesity in the U.S. in 2002 dollars is \$117.1 billion, and, with estimates that obesity could affect two in five adults by the year 2025, the need to address obesity at an early age is clear.

It has been shown that the nutritional and behavior modifications necessitated by bariatric surgery, as evidenced by the reported success of the gastric bypass procedure in adolescents, are safe, and are associated with significant weight loss as well as correction of co-morbid conditions and improved self-image and socialization [3-5]. The use of the Lap-Band System results in clinically significant weight loss with significantly less operative morbidity and mortality than the gastric bypass procedure in adults [6]. Additionally, the adjustability to patient needs and the relative ease of reversal is unique to the Lap-Band System. This system has been used in adults in Europe and other countries since 1993; international publications report a mean Percent Excess Weight Loss (%EWL) of 52% in subjects with 1 year of follow-up and 68% after 2 years of follow-up [7-9]. In the first US clinical study a mean of 34.6% EWL in 221 subjects was reported with 1 year follow-up and 38.2% EWL in 122 subjects at 2 years of follow-up. However, the first published US experience by Rubinstein of 63 patients showed a 53% EWL at 3 years [10]. Currently, our experience in adults demonstrates a 44.3% EWL at 1 year [11]. Finally, the Lap-Band has been shown to be a safe and effective method of weight loss in morbidly obese adolescents by Dolan, et.al., in Brisbane, Australia [12]. In fact, when compared to matched controlled adults, adolescents did better in terms of weight loss and complications [13]. Mortality has been found to be only about 1 in 10,000 [0.01%]; this compares with a mortality rate among gastric bypass patients that approaches 0.5% [6].

At this time, there is only one surgical option for morbidly obese adolescents: Roux-en Y gastric bypass. We believe that the LAP-BAND®, which can be removed after sufficient weight loss and behavior modification, would be a better option for adolescents.

The lower age limit of children being offered LAGB surgery is open to conjecture. One of the obvious concerns in offering surgery to children as young as twelve years of age is the effect surgery may have on the child's growth. However, there are data available that encourage this concept. Obese children are known to grow faster than non-obese children [14-16]. They are taller by at least one standard deviation than their normal weight peers before puberty, and then normalize in their late teens. Furthermore, they have higher levels of lean body mass, as well as fat mass, corresponding with their height. Obese girls achieve puberty at a younger age than non-obese girls [17-19]. Also, it is typical for morbidly obese children to be taller than average, have heavier muscle mass, and for girls to be sexually developed by the age of 12.

In contradistinction to Roux-en Y Gastric Bypass (RYGB) and intestinal bypass procedures such as the biliopancreatic diversion (BPD) and duodenal switch, LAGB patients suffer no nutritional sequelae after surgery [20-23]. There has been no study that describes any nutritional deficiency after LAGB, despite a reduction in fat mass by up to 50%. In the first 3 months post-surgery, there is a small reduction (5-10%) in lean body mass, which stabilizes at 6 months, with no prolonged loss of lean mass thereafter [24-25]. The greatest disparity between LAGB and RYGB or BPD is in Vitamin D and calcium metabolism, which has only been studied in adults. Coates et al has recently shown increase in bone turnover and decreased bone mass 9 months after RYGB [26]. Newberry et al showed that after intestinal bypass operations, 50% of patients were depleted in Vitamin D, with associated hyperparathyroidism in 63% [27]. In concert with the data showing no caloric or nutrient malabsorption after LAGB, Pugnale et al showed no evidence of secondary hyperparathyroidism 1 year after LAGB [28]. The adult population effectively eat approximately 1200-1800 calories per day after LAGB, which equates with caloric intake of non-obese adults, and this would presume to be the same in children. In addition, all micronutrients and vitamins are completely absorbed.

There is an excellent opportunity in this proposed protocol to study the effect on growth of weight-loss after surgery in morbidly obese children as young as 14 years. Given that there is no evidence of nutritional sequelae or interruption of bone growth after LAGB and since we will be performing nutritional monitoring and bone density studies, there would seem to be minimal risk in including these younger children in the protocol.

1.2 Description of LAP-BAND® System Components

The implanted components of the Lap Band System include:

1. ADJUSTABLE BAND

The adjustable band component is a 13-mm wide band available in three sizes (an inside circumference of 9.75 cm, 10 cm, or 11 cm), which forms a circular ring around the stomach when closed. The band is made of silicone elastomer and the inner surface of the band is inflatable, allowing for stoma adjustments. Radiopaque, kink-resistant tubing is used to connect the inflatable section to the access port.

2. ACCESS PORT

The access port consists of a 31 mm-diameter titanium reservoir in polysulfone housing with a high-compression silicone septum. It is used for percutaneous adjustments of stoma diameter and is self-sealing when penetrated with the access port needle. The access port is also supplied individually packaged.

A component of the system used for adjustments post-operatively:

3. ACCESS PORT NEEDLE

The access port needles are a 20 gauge and a 22 gauge, 38 mm (1.1/2 inch), non-coring, deflected tip ("Huber Needle") needle designed to penetrate the access port for saline volume adjustment of the LAGB System. The access port needle is also available individually packaged in packs of 10 for additional stoma adjustments via the access port.

2.0 STUDY OBJECTIVES

2.1 Primary Objective

The primary objective of this research is to demonstrate the safety and efficacy of the use of the LAP-BAND® System in the morbidly obese adolescent population in the United States, and therefore provide these individuals with a significantly less morbid and reversible surgical option for weight loss.

2.2 Secondary Objective

The secondary objective is to assess the status of co-morbidities and changes in quality of life and the academic performance from baseline.

3.0 INVESTIGATIONAL PLAN

3.1 Study Design

This is a prospective, non-randomized, single-center study to be conducted under an FDA-approved Investigational Device Exemption (IDE). One investigational site will enroll and treat up to 120 subjects who meet the criteria for use of the LAP-BAND® System, except that they are adolescents ages 14 to 17. Subjects will be followed for five years.

3.2 Study Population

3.2.1 Inclusion Criteria

1. Be at least 14 and less than 18 years of age at the time of enrollment into the study, at Tanner developmental stage 4 or greater, and be past the point of peak height velocity. Bone age will be determined in this evaluation.
2. Have a BMI of at least 40 [BMI is calculated as follows: $BMI = \text{weight (Kg)} / (\text{height (m)}^2)$; i.e. (W/H²) or Kg/m²]. These criteria are the ones recommended by the NIH for adults. When applied to adolescents, they are more conservative than the criteria of BMI > 95th percentile for age because of the BMI curves for children and adolescents. We feel the criteria proposed in Pediatrics, 2004;114(1):217-223 are unnecessarily restrictive given the incidence of comorbidities starting at a BMI of 35, the likelihood of the development of comorbidities starting at a BMI of 35, and the poor results of therapies which do not include bariatric surgery for adolescents with a BMI of 35 or greater.
3. Have a history of obesity for at least 5 years, including failed attempts at diet and medical management of obesity.
4. Express willingness to follow protocol requirements which include signing an assent form, having the individual's legal guardian sign a consent form; completing 1-2 week, 6 week, 3 month, 6 month, 9 month, 12 month, and every 6 month follow-up visits for a total of five years, and completing all protocol-required laboratory and diagnostic tests.
5. Confirmation by a psychologist or psychiatrist experienced with adolescents that the subject is sufficiently mature emotionally to comply with the study protocol.

6. Assure investigators that subject, if female of childbearing potential, is using an appropriate form of contraception.

3.2.2 Exclusion Criteria

1. Intention or need to have another surgical procedure for weight reduction within 12 months of Lap Band placement.
2. History of congenital or acquired anomalies of the G.I. tract, such as; congenital or acquired intestinal telangiectasia, Crohn's disease or ulcerative colitis; severe cardiopulmonary disease or severe coagulopathy; hepatic insufficiency or cirrhosis.
3. Presence of dysphagia or documented esophageal dysmotility.
4. Patients with autoimmune connective tissue disorders.
5. Patients with acute abdominal infections.
6. Pregnancy or intention of becoming pregnant in the next 12 months.
7. Presence of psychiatric problems or immaturity which would compromise cooperation with the study protocol.
8. History of previous bariatric surgery, intestinal obstruction or adhesive peritonitis.
9. Presence of localized or systemic infection at the time of surgery.
10. Chronic use of aspirin and/or non-steroidal anti-inflammatory medications and unwillingness to discontinue the use of these concomitant medications.
11. History of gastric or esophageal surgery.
12. Use of weight loss medications simultaneously

3.2.3 Patient selection equitability

We acknowledge the importance of equitability of research subjects in relation to patients' financial circumstances. Therefore, we will cover all costs for up to twenty percent of the study subjects who are unable to pay for professional fees, device fees and hospital costs and study-related costs.

Our staff will make every effort to obtain pre-authorization from the patient's insurance company for the surgery. If the insurance company refuses to pay the fees, the patients will be charged for the surgery and anesthesia. All study-related costs will be charged to the subject's family. Subjects and their parents will be notified of the payment arrangement very early on in the recruitment process. In the event that sufficient funds become available, we will cover all costs for whatever number of patients can be supported by these funds. We are actively seeking philanthropic funding to allow as many morbidly obese adolescents access to the study as possible.

3.2.4 Removal of Subjects from the Trial

A study subject or the parent of the study subject may end their participation in the study at any time. If a subject withdraws, the principal investigator will make reasonable effort to determine the reason for the subjects' withdrawal from the study and complete termination procedures as described in section 3.4.7. Telephone calls, registered letters and offers of transportation to the investigational site are considered reasonable effort.

In addition, the principal investigator may discontinue a patient's participation in the study if the patient fails to comply with the follow-up evaluation schedule (i.e., if patient missed 3 or more sequential follow-up visits.)

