3.3 Study Duration

Subjects will be followed for a period of five years post-operatively.

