3.4.6 Diet

- No calorie-specific diets
- No weight loss medications
- Eat slowly and chew thoroughly
- Stop eating when full

3.4.6.1 POST OP Week 1 and 2
Liquids only moving to full liquids**3.4.6.2 POST OP Week 3 and 4**
Blended diet with puree foods
Do not drink with meals**3.4.6.3 POST OP Weeks 5 and 6**
Soft Diet
Do not drink with meals**3.4.6.4 POST OP Week 7 and beyond**
No texture restrictions
Well balanced low-fat diet
Do not drink with meals
Include high fiber and high protein foods
Three small meals everyday
Drink 8 cups of liquid everyday**3.4.7 Termination**

If a subject decides to withdraw from the study and desires the Lap-Band removed, this will be done using laparoscopic techniques when possible. The appropriate follow-up care will be provided for those cases, including hospital and clinic follow-up when necessary. In these cases, upper gastrointestinal studies will be performed when necessary.

After the five-year study is complete, subjects have the option of having the band surgically removed or keeping the band. If the subject chooses to keep the band, they will be followed with office visits every six months.

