3.6.2 Adverse Event Recording

Adverse events are intended to be volunteered by subjects or observed by the investigator. All adverse events are to be recorded on appropriate case report forms. The investigator is instructed to report any serious adverse event immediately to the IBRA.

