3.7.7 Data Collection

Data will be collected by the principal investigator, the nurse practitioner, or nutritionist and documented on a standardized data form. The data will be entered by a research coordinator or the principal investigator in a fashion that maintains patient anonymity, using a unique identification number. The data will be entered into a secure computerized database, which can be accessed only by the principal investigator and the research coordinator with the use of a password. Data collection and statistical analysis will be performed by assigned research personnel, who will access the data using the unique patient identification number assigned.

We will collect relevant life history information from the subject's medical records including illnesses and hospitalizations that occur while subjects are participating in the research, as well as age, ethnic background, marital status, medical history, weight loss, changes in weight-related medical conditions, and information about the surgery and information about lap-band adjustments, and complications. We will collect medical information from physicians and other healthcare providers in General Surgery, Pediatric Surgery, Pediatrics, Psychiatry, and Psychology and from the NYU hospital medical records.

All data will be recorded on case report forms and compared at 6, 12, 24, 36, 48, and 60 months with baseline. Results will be reported descriptively as well as by modeling weight loss in order to assess aggregate outcomes and address the issues of safety and efficacy.

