3.7.8 Stopping Rules For Adverse Events

The trial will be terminated if two or more patients die due to the surgery. The trial will be terminated if during the follow-up period two or more of the first 25 patients implanted have developed esophageal dilation. The trial will also be terminated if during the follow-up period two or more of the first 35 patients implanted develop a nutritional deficiency.

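### No vital-status or band-status contact is scheduled to month 60 for a subject who withdraws or is discontinued early with the band in place, so late deaths, removals and reoperations can be undercounted

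*Combined protocol and SAP*

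**What the plan says.** Follow-up is set at five years: "Subjects will be followed for a period of five years post-operatively" (3.3).

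Section 3.2.4 gives two ways to leave early. A subject or parent may withdraw at any time. The investigator may, but need not, discontinue a subject "if the patient fails to comply with the follow-up evaluation schedule (i.e., if patient missed 3 or more sequential follow-up visits"). For withdrawals the investigator must make a reasonable effort to learn the reason and "complete termination procedures as described in section 3.4.7". Telephone calls, registered letters and offers of transport to the site count as reasonable effort.

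Section 3.4.7 has two paragraphs. The first begins "If a subject decides to withdraw from the study and desires the Lap-Band removed" and provides removal and aftercare for those cases. The second concerns the period once the five-year study is over. It is there that the protocol says "If the subject chooses to keep the band, they will be followed with office visits every six months".

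On ascertainment, 3.6.2 states: "Adverse events are intended to be volunteered by subjects or observed by the investigator". Section 3.7.7 collects from medical records "illnesses and hospitalizations that occur while subjects are participating in the research". The same sentence also lists complications, and the next one names other providers and the NYU hospital records; neither is expressly limited to the time of participation. Table I has no column for contact after early exit.

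**The concern.** Safety is half of the primary objective (2.1), and the device stays in the body unless it is removed. Section 3.6.1 lists gastric prolapse, band erosion, tubing failure, port migration and explantation among post-operative events, and several of these can occur late. A subject who leaves with the band in place remains at risk of them, but no contact is scheduled at which they would come to light.

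A count of removals or reoperations among implanted subjects can then err in one direction only. A rate per observed person-year avoids that bias only if leaving is unrelated to risk. That is doubtful where a subject stops attending because the band failed or was removed elsewhere. The plan also does not ask for the number of implanted subjects whose status is known at month 60, so a reader of the results could not judge how complete the counts are.

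**Working it through.** **Step 1: who is covered after leaving.**

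| Situation | Provision | Later status contact to month 60 |
|---|---|---|
| Withdraws, wants band removed | 3.4.7, first paragraph | Aftercare as needed |
| Withdraws, keeps band | 3.2.4 exit effort only | None stated |
| Discontinued for missed visits, keeps band | None stated | None stated |
| Completes five years, keeps band | 3.4.7, second paragraph | Not applicable (six-monthly visits follow) |

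The gap is in the second and third rows.

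**Step 2: time left after discontinuation.** Section 3.4.5.1 sets 14 visits: weeks 1–2 and 6, months 3, 6, 9 and 12, then every six months to 60. If the investigator discontinues at the third missed visit:

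| Last seen (month) | Third miss (month) | Months left to 60 | Share of 60 |
|---|---|---|---|
| 6 | 18 | 42 | 70% |
| 12 | 30 | 30 | 50% |
| 24 | 42 | 18 | 30% |
| 36 | 54 | 6 | 10% |

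For subjects last seen at month 12 or later, 18 months of missed visits come first. During that time the subject is still enrolled and adverse event reporting still applies. The earliest possible third miss is month 3.

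**Step 3: person-years unobserved.** The documents give no loss rate. Assume that a fraction f of 120 subjects leaves evenly over five years, losing 2.5 years each on average. Planned person-years are 120 × 5 = 600. Lost person-years are 120 × f × 2.5.

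| f (assumed) | Lost | Observed | Share lost |
|---|---|---|---|
| 10% | 30 | 570 | 5% |
| 25% | 75 | 525 | 12.5% |
| 40% | 120 | 480 | 20% |

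**Step 4: events unseen, at most.** Assume a constant removal or reoperation rate of 3% per year (range 1% to 5%); the documents give none. Expected events are 600 × 0.03 = 18 (6 to 30). If no record source captured any event after exit, 0.03 × 30, 75 or 120 = 0.9, 2.25 or 3.6 would be unseen. Over the whole range this is 0.3 (1% rate, 10% loss) to 6.0 (5% rate, 40% loss). Any event found through 3.7.7 records lowers these figures.

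**Step 5: if leaving is related to risk.** Suppose the rate doubles after departure (assumed). The missed share is 2 × lost / (observed + 2 × lost): 60/630 = 9.5%, 150/675 = 22% and 240/720 = 33%, again before any capture from records.

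**Step 6: precision.** With no events, the two-sided 95% Poisson upper limit is 3.689 divided by person-years: 0.61 per 100 person-years at 600, and 0.65, 0.70 or 0.77 at 570, 525 or 480. The plan does not itself promise a rate per person-year, so this only shows scale.

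**The case against.** **There is contact at exit.** For withdrawals, 3.2.4 requires effort both to learn the reason and to complete termination procedures, with transport offered. Status at exit could well be learned then. This stands: a reader might infer that leavers get no contact at all, and for withdrawals the text says otherwise. What is missing is any contact afterwards.

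**Records may fill part of the gap.** The provider and hospital records in 3.7.7 carry no express limit to the time of participation, and some bands will be revised or removed at the implanting centre. This also stands, and it makes the counts in Step 4 upper bounds under their assumptions. However, 3.7.7 sets no schedule or trigger for looking up someone who has left.

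**Discontinuation is discretionary.** A non-attender need not be removed. While subjects are enrolled, adverse event and SAE reporting and the external safety surgeon apply (3.6.1, 3.6.3, 3.7.10). True, so the point is confined to the time after departure.

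**Permission may lie elsewhere.** The consent pages are not available for this review and may already allow later contact. The point concerns the protocol text.

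**The stopping rules.** A reader might infer that the gap disables 3.7.8. The documents do not support that. The death rule, "The trial will be terminated if two or more patients die due to the surgery", has no time limit. The band mortality figure in 1.1 (1 in 10,000, with no stated window) gives 120 × 0.0001 = 0.012 expected deaths. The other two rules concern esophageal dilation, monitored by esophagram, and nutritional deficiency, monitored by blood work and nutritional evaluation. A call or letter cannot detect either, so those rules neither support this remedy nor gain from it.

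**Yield.** People who have withdrawn or missed three visits in a row will be hard to reach, so the check would recover only part of what is missed.

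**Conclusion.** The point holds as a gap in follow-up. A subject can leave early with the band in place, and nothing in the protocol schedules a check of vital or band status after that. Counts of late deaths, removals and reoperations per implanted subject can therefore only be too low.

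The size is uncertain. Under an assumed even loss of 10% to 40% and a constant event rate, up to 5% to 20% of events would be unseen; the ceiling rises to 9.5% to 33% if risk doubles after departure. The loss, timing and event rates are all assumptions.

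The effect falls on late device events. It would go too far to conclude that the weight-loss analysis in 3.7.6 is invalid, since nothing here shows that. This is a cheap improvement worth making.

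**What to change.** **1. In 3.2.4 and 3.4.7, add:**

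> Discontinuation for missed visits ends study visits but not safety follow-up. For every implanted subject who has left, vital status and band status (in place, revised or removed) will be sought once a year to month 60, by telephone, letter or existing hospital records. Subjects who withdraw will be asked to permit this.

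**2. In 3.7.5, add:**

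> Deaths, band removals and reoperations to month 60 or last contact will be reported with the number implanted, the number with known vital status and band status at month 60, and the person-years observed.

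No change to 3.7.8 is needed.

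**Cost.** Two short text additions, possibly one line in the consent and assent forms, and review of the amendment. At one contact per departed subject per year, the assumed loss means 12 × 2.5 = 30 to 48 × 2.5 = 120 contacts over the study. The second item needs no new contact. Some subjects will refuse or not be reached, so ascertainment will stay incomplete. The known-status denominators will at least show by how much.
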